[name] developed a web-based intervention (mehealth for ADHD) which enables community-based pediatricians to deliver higher quality ADHD care⁴⁴ leading to children with significantly fewer ADHD symptoms. 45 Subsequently, partnerships with the American Academy of Pediatrics and American Board of Pediatrics helped spread use of the portal beyond practices that participated in research and now includes 60,801 patients cared for by 2,153 pediatricians in 886 practices across the US. These practices use the portal as a registry to manage their entire ADHD patient population. With pediatricians continuing to enroll patients on the portal as part of routine clinical care, opportunity exists to leverage this infrastucture to efficiently develop and test new interventions. The proposed research would fill a sizable gap as the current portal is focused exclusively on young school age children with ADHD and medication adherence has not been targeted nor improved. Specifically, while a randomized controlled trial testing the efficacy of the mehealth for ADHD web intervention demonstrated significant effects on children's treatment outcomes, there was not a significant intervention effect on medication adherence (i.e., 59% of days covered by children in the mehealth for ADHD portal group vs. 54% in the control group). 45 Moreover, the portal is devoid of features for adolescents. In focus groups, pediatricians, parents, and adolescents have repeatedly requested such features.

STUDY DESIGN:

We will conduct a pilot, single-arm, open-label trial of the medication experiment feature among 30 adolescents experiencing uncertainty about continued medicine use (see **Figure 2**). Because the medication experiment feature is not clinically relevant for adolescents taking a non-stimulant ADHD medication, they will be excluded. At the time of enrollment, families will complete baseline measures electronically and schedule an in-person visit. We will verify the medication prescribed and the number of days covered with medicine in the past year using

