At the conclusion of the medication experiment, the research assistant will schedule an inperson study visit at the Center for ADHD. The study physician, adolescent and parents will discuss what was learned using a report generated by mehealth for ADHD to visualize the outcome data that was collected. Subsequently, the adolescent and parent will be asked to independently indicate their preference for what to do next (continue [medication regimen from experiment], resume previous medication/dosage, conduct another experiment, return to pediatrician to adjust dosage or change medication, other), and their preferred role in decision-making. The study physician will then facilitate a discussion to resolve any differences between adolescent and parent preferences and come to a consensus. The parent will receive a study summary document to share with their child's pediatrician so s/he is aware of what was learned and can use this to guide future management decisions. The adolescent and parent will report this decision, their certainty about the decision, their preferred role in decision-making, their involvement in the process of making this decision, and their intentions about taking/giving medicine. We will also ask the parent and adolescent about the usability the medication experiment software (see Measures).

Measurement Strategy: Aggregation of individual trials to estimate a population level treatment effect isn't needed given the strong evidence of stimulant effectiveness among adolescents.¹ Rather, it is important to ascertain whether the use of medication experiments helps adolescents and parents work together to resolve uncertainty about future use of medicine. We will describe the type and number of medication experiments conducted as well as the personal outcomes selected for tracking. We will examine process outcomes like the decision-making involvement, comfort with the decision made, and whether the decision was implemented.

Measures to characterize the sample on demographic, ADHD, and psychosocial factors

- 1. Demographics: Adolescents, parents, and pediatricians will report on age and race/ethnicity. Parents will also report on child insurance status, and their own level of education and mental health history.

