- 9. Implementation factors of UTBC influencing medication continuity (See Compendium of Measures):): These factors will be measured using the Adolescent and Parent Medication Barriers Scales (AMBS and PMBS). 47, 48 Adolescents and parents respond using a 5-point Likert-type scale with ratings from "strongly disagree" to "strongly agree" to report perceived barriers to medication taking. Both the adolescent scale (17-items) and parent scale (16-items) have strong internal consistency for total score and the four factor-analytically derived subscales: 'Disease frustration/adolescent issues', 'Regimen adaptation/cognitive', 'Ingestion issues', and 'Parent reminder'. For criterion-related validity, adolescents classified as non-adherent had significantly higher barrier scores than those classified as adherent. In prospective validation studies, the adolescent-perceived barriers of 'Disease frustration/adolescent issues' and parent-perceived barriers of 'Regimen adaptation/cognitive issues' were associated with poorer adherence to medication taking. 48
- 10. Past Year Medication Continuity: We will calculate the percentage of days covered with medicine based pharmacy dispensing records. We have successfully obtained pharmacy dispensing records via parental permission for 95% (155/164) of subjects across 2 studies (R01 MH074770, K23 MH083027).^{63, 64} Pharmacy dispensing records provide an objective, unobtrusive, reliable measure that is a well-accepted proxy for medication consumption⁶⁵ that was significantly correlated with the more expensive and invasive Medication Event Monitoring System (MEMSCapTM) which uses a microprocessor in the medication container cap to record the day and time of each vial opening.⁶⁶
- 11. Medication Diversion: Adolescent self-report of giving away, trading, or selling ADHD medicine to someone for whom it was not prescribed will be collected via a confidential web-based survey used in past population-based studies of middle/high school students. 67, 68

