- 13. Certainty about the decision will be measured using the Decisional Conflict Scale (DCS): The DCS⁷⁰ has an initial question to ascertain the option that has been selected. Options presented will be: continue [medication regimen from experiment], resume previous medication/dosage, conduct another experiment, return to pediatrician to adjust dosage or change medication, other [write in]. The DCS then has 16 questions that are divided into five subscales: informed subscale, values clarity subscale, support subscale, uncertainty subscale, and an effective decision subscale. The informed subscale measures how informed participants feel about the benefits and risks of the decision. The values clarity subscale measures a participant's feelings about personal values for benefits and risks/side effects. The support subscale measures perceived levels of support during decision-making. The uncertainty subscale measures a participant's level of certainty about the best choice to make. The effective decision subscale measures the satisfaction with the decision made. The total DCS score equally weighs all five subscales. Responses to each question are reported on a 5-point Likert scale (0 = strongly agree to 4 = strongly disagree). The total DCS scores are calculated by summing item scores and then converting the scores to a 0-100 scale, where 0 implies no decisional conflict and 100 implies extremely high decisional conflict. Scores <25, 25 to 37.5, >37.5 indicate low, moderate and high decisional conflict, respectively. Scores 25 and higher reflect clinically significant decision conflict.
- 14. Behavioral Intention questions that will assess the adolescent and parent intention to take/give ADHD medicine regularly will be measured using the standard measure of intention from the UTBC. 46 Responses are on a 7-point scale from strongly agree (+3) to strongly disagree (-3) that assess intention to take medicine for ADHD on weekdays, weekends, and school vacations.
- 15. System Usability Scale (SUS)⁷¹ is a validated 10-item unidimensional scale with response options on a 5-point agreement scale which results in a score from 0 to 100, with higher scores indicating greater usability.

Implementation of decision: 3 months after study visit 2, we will obtain pharmacy dispensing records to ascertain whether their joint decision was implemented. If medication was continued, we will calculate the percentage of days covered.

DATA ANALYSIS

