We will conduct descriptive analyses to summarize measures that characterize the sample in terms of demographic, ADHD, and psychosocial factors, the experiments selected, and decisions made, as well as feasibility and usability data. In order to determine overall feasibility and usability of our pilot intervention, we will compare retention, participation, and usability ratings to a priori criteria based on previous research (i.e., retention $\geq 80\%$, participation $\geq 80\%$, usability ≥ 70), 72 using Chi-square tests.

Power and Sample Size

We selected a target sample size of 30 to exceed the recommended sample size (n = 20) for a pilot trial designed to inform a larger efficacy trial with 80% power to detect a medium effect. Of note, we aren't powering the study to examine differences in outcomes by experiment type. Paired-samples t-tests will be used to calculate the change in DMIS,DCS, and behavioral intentions for all adolescents and parents, and for medication continuity among the subset who choose to continue medication after completing their experiment. Cohen's d will be calculated to estimate effect size for each pre- to post-outcome and interpreted as small (.20), medium (.50), and large (.80).

Hypothesis testing

We will test the following hypotheses:

- 1. From pre to post, within-subject report on DMIS subscales "child express" will increase and "parent seek" will increase.
 - a. Paired sample t-test
- 2. From pre to post, within-subject DCS will decrease.
 - a. Paired sample t-test
- 3. Higher post-DMIS joint/decision scores will be reported by dyads who differ on initial preferences following the experiment compared to those who don't.
 - a. Two sample t-test
- 4. Higher post-child express scores will be reported by adolescents who want to make the decision alone compared to those who prefer to share decision or have parent make decision.
 - a. Two-sample t-test
- 5. Adolescent-parent conflict as measured at baseline by the CBQ will be positively associated with discordance in independent preferences following the medication experiment.
 - a. Biserial correlation coefficient
- 6. The difference between the adolescent's intention to take ADHD medication and the parent's intention to give ADHD will decrease from pre to post.
 - a. Linear mixed model

Scientific Rigor:

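### The planned continuity t-test most naturally sets a full year of coverage against about three months, so unchanged seasonal use can appear as change; a season-matched comparison should be reported beside it

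*Combined protocol and SAP*

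**What the plan says.** In the combined protocol and SAP, the Power and Sample Size section applies paired t-tests to several pre-to-post outcomes and adds one "for medication continuity among the subset who choose to continue medication after completing their experiment". Cohen's d is to be computed for each pre-to-post outcome and labelled small, medium or large.

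Two continuity values are defined elsewhere.

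- **Before.** Study Design says dispensing data will verify "the number of days covered with medicine in the past year". Item 10 of the measures, whose title refers to the past year, says "We will calculate the percentage of days covered with medicine based pharmacy dispensing records". It sits under the heading "Measures to characterize the sample on demographic, ADHD, and psychosocial factors", not under Outcome Measures.
- **After.** The paragraph on implementation of the decision says "3 months after study visit 2, we will obtain pharmacy dispensing records to ascertain whether their joint decision was implemented", and then "If medication was continued, we will calculate the percentage of days covered". This dates the retrieval of the records; the coverage window is only implied.

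The plan is aware that use varies over the year. The Intervention section gives stopping over the summer as an example of a recent medication decision, and the behavioral intention items "assess intention to take medicine for ADHD on weekdays, weekends, and school vacations". Under Duration, families may set the start and end of their experiment. The Intervention section steers experiments towards the middle of the school year. No section mentions season in connection with the coverage windows.

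**The concern.** A past-year window always contains one summer. A three-month window may contain none, part or most of one. For an adolescent who takes medicine in term and stops every summer, the two percentages differ even if nothing about that behaviour has changed. If visit 2 dates cluster in one part of the year, these differences share a sign and do not average out.

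At stake is a mean change and a Cohen's d that mix calendar with behaviour, in a pilot meant to inform a larger trial. A d with a verbal label attached is easily carried forward as evidence of benefit or harm.

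**Working it through.** The plan gives no SD, effect size or power for continuity, so there is no figure of its own to reproduce.

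**One adolescent, use unchanged.** Assume cover every day except a 70-day summer stop.

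- Past year: (365 − 70)/365 = 80.8%.
- A 91-day window wholly in term: 100%, an apparent change of +19.2 points.
- A 91-day window holding the whole stop: 21/91 = 23.1%, an apparent change of −57.7 points.

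**Group mean, use unchanged.** Let *p* be the share of summer-stoppers, *c* their coverage outside the stop, and *k* the mean number of stop days in the 91-day window. With a 75-day stop,

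artefact = *p* × *c* × (75/365 − *k*/91).

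Assumed inputs: *c* = 60%, near the 54% and 59% of days covered that the background section reports from an earlier trial; *p* = 25% or 50%, for which the documents give no figure. *k* is averaged over every possible visit 2 day in the stated months, with the stop starting on 1 or 15 June.

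| Visit 2 dates (assumed) | Stop starts | *k* | Artefact in points, *p* = 25% / 50% |
|---|---|---|---|
| November–February (follow-up wholly in term) | either | 0 | +3.1 / +6.2 |
| November–April | 15 June | 5.7 | +2.1 / +4.3 |
| November–April | 1 June | 9.8 | +1.5 / +2.9 |
| January–May | 15 June | 19.4 | −0.1 / −0.2 |
| January–May | 1 June | 26.3 | −1.3 / −2.5 |
| Even over the year | either | 18.7 | 0 / 0 |

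First row at 25%: 0.25 × 60 × 0.2055 = 3.1. Fifth row at 25%: 0.25 × 60 × (0.2055 − 0.2892) = −1.3. Even dates give *k* = 91 × 75/365 = 18.7, which cancels exactly. The artefact is proportional to *c*: at the 50% of days covered also cited in the background, the first row becomes +2.6 / +5.1. With no summer-stoppers it is zero.

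**Season-matched baseline.** Use the same calendar months one year before follow-up. If the seasonal pattern repeats and use is otherwise stable, the expected change is 0. Simulation with 20 continuers gave mean changes within 0.1 point of zero and about 5% rejection at a two-sided 0.05 level, which is assumed because the plan states none.

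**Price of matching.** In the same simulation (independent monthly fills, coverage SD 20 points), the SD of the change in term was 29.2 points unmatched and 36.5 matched.

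- Standard errors at n = 20: 29.2/√20 = 6.5 and 36.5/√20 = 8.2.
- Root mean square error in term, unmatched: √(3.1² + 6.5²) = 7.2 at 25% stoppers and √(6.2² + 6.5²) = 9.0 at 50%. Matched: 8.2 in both.
- Break-even bias: √((36.5² − 29.2²)/20) = 4.9 points. One stopper contributes 60 × 75/365 = 12.3 points, so this is 4.9/12.3, or about 40% stoppers.
- With even dates, root mean square error was 6.6 unmatched and 7.9 matched.

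A second model with 30-day fills and random gaps had smaller SDs (about 19 and 23) and broke even at about 25% stoppers.

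**The case against.** The strongest reply is that this is a small gap in wording. The baseline look-back is named as the past year, so the plan is not silent on windows. What is missing is the explicit link to the t-test, exact dates, and the follow-up window. The 12-against-3-month pairing is an inference, although no other pairing is available from the measures as defined. All of this stands. So does the point on consequence: continuity is a secondary quantity in a single-arm pilot, and whether the decision was implemented is ascertained separately.

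Three stronger readings are tempting and are not supported.

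- A reader might infer that the mid-school-year steer makes a false increase, of roughly the size the plan calls small, the likelier result. That steer governs the experiment. Follow-up opens only at visit 2, after the experiment, and can run into summer. The table shows the sign turning between November–April and January–May, and the visit dates are unknown.
- A reader might infer, from the sentence that coverage is calculated if medication was continued, that the subset is selected on the outcome. The analysis section already defines it by choice, and the other sentence can be read as saying only when the percentage is computed.
- A reader might infer that the past-year baseline should be replaced. The error figures above do not support that: matching removes seasonal bias but often raises total error.

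**Conclusion.** The point holds as a minor one. Followed as written, the plan most naturally compares a window that always includes a summer with one that may not, and it has no check on what this does to the change. Unchanged use can appear as change if follow-up windows cluster in a season.

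Direction and size cannot be determined from the documents. Under the stated assumptions the expected artefact runs from about −2.5 to about +6 points, and is zero with evenly spread dates. Follow-up wholly in summer would give a larger fall, but nothing in the protocol suggests that all visits would be timed that way. The result rests on the assumed share of stoppers, length of stop, coverage and visit dates. The mechanism rests only on some adolescents stopping over the summer, which the protocol treats as a known decision.

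**What to change.** 1. State that the follow-up coverage window is the 3 months after study visit 2, and that past-year coverage is the baseline paired with it.
2. Define continuers by the joint decision recorded at visit 2, as the analysis section already implies, and not by later fills. Say in advance how each recorded option counts. The list begins "continue [medication regimen from experiment], resume previous medication/dosage, conduct another experiment", and continuing the experiment's regimen after a trial off medicine can mean taking none.
3. Beside the change from past-year coverage, report a season-matched change. Its baseline is the same calendar months one year before follow-up, with the same denominator and carry-over rule in both windows. Those months lie inside the past-year records, because visit 2 follows enrolment and participation lasts up to 4 months. Fills available for carry-over into that baseline reach back only as far as the time from enrolment to visit 2; note where this is short.
4. Label both changes descriptive, and do not read Cohen's d as a benefit unless the two versions agree.

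The cost is a few sentences and modest programming, with no new data. The matched estimate is noisier and does not remove age-related decline. Its window midpoints are 12 months apart, against 6 + *g* + 1.5 = 7.5 to 11.5 months for the past-year baseline, where *g* is the 0 to 4 months from enrolment to visit 2. An assumed fall of 5 points a year would show as −5.0 matched, against −3.1 to −4.8 unmatched. It should therefore be added to the past-year comparison and not replace it.

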Decision-Making Preferences—The Control Preferences Scale⁶⁹ assesses the degree of control an individual wants to assume when decisions are being made about medical treatment. The Control Preferences Scale will be modified so that adolescents and parents choose preferred control options that range from the adolescent solely making the decisions regarding choice of medication experiment, to the adolescent making the decisions jointly with the parent, to the parent solely making the decisions.

Outcome Measures

- 12. Decision-Making Involvement Scale (DMIS) (Miller et al., 2012): is a 30-item scale to measure adolescent involvement in a decision. The five subscales are: "Child Seek" (child asks for an opinion or information from parent), "Child Express" (child expresses an opinion or information to parent), "Parent Seek" (parent expresses advice or opinion to child), "Parent Express" (parent expresses advice or opinion to child), and "Joint/Options" (negotiation or brainstorming between parent and child). We will use the Decision-Making Involvement interview guide to collect this measure at study visit 1 and the stand-alone version to collect it study visit 2.

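### Hypotheses 3 and 4 compare visit 2 DMIS scores between self-selected groups and leave the visit 1 scores unused, so they cannot separate a difference tied to the post-experiment decision from one already there

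*Combined protocol and SAP*

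**What the plan says.** All references are to the combined protocol and SAP.

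- **Hypothesis 3** (Data Analysis, Hypothesis testing): "Higher post-DMIS joint/decision scores will be reported by dyads who differ on initial preferences following the experiment compared to those who don't". The method is a two-sample t-test.
- **Hypothesis 4** (same list): "Higher post-child express scores will be reported by adolescents who want to make the decision alone". The comparison group is all other adolescents, whether they favour a joint choice or leave it to the parent. The method is again a two-sample t-test.
- **Hypothesis 1** (same list) takes the within-subject change in Child Express and Parent Seek by paired t-test. Power and Sample Size plans paired tests of DMIS change for all adolescents and parents.
- **Outcome Measures, item 12 (DMIS):** "We will use the Decision-Making Involvement interview guide to collect this measure at study visit 1". The stand-alone version is used at visit 2.
- **Intervention:** at visit 1 the DMIS is anchored to the family's most recent ADHD medication decision. At visit 2 participants report involvement in the decision just reached after the experiment.
- **Power and Sample Size:** the target of 30 is set against a recommended size for a "pilot trial designed to inform a larger efficacy trial with 80% power to detect a medium effect". No alpha, sidedness, group split or power is given for Hypotheses 3 or 4.

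**The concern.** Neither grouping is randomised. Dyads sort themselves by whether their preferences differ after the experiment, and adolescents by the decision role they want. The plan itself gives reasons to expect such groups to differ beforehand:

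- Hypothesis 5 predicts that baseline parent-adolescent conflict (CBQ) goes with discordant preferences, which is the grouping variable of Hypothesis 3. The CBQ measures conflict and negative communication, so the plan expects these groups to differ at baseline in how they talk to each other. That could either mimic or mask a difference in negotiation at visit 2.
- The background reports that adolescents' responsibility for medication grows with age and maturity, and eligibility spans ages 11 to 15. Adolescents who want to decide alone may already have been the more outspoken ones.

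A significant result could then describe these families in general rather than how they made this decision. The visit 1 scores that would help separate the two are collected but not used in these tests.

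**Working it through.** **Plan's own figure.** The target of 30 comes with no inputs, and no power is stated for these two hypotheses, so there is nothing to reproduce.

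**Inputs.** From the plan: N = 30, and d = 0.5 as its label for a medium effect. Assumed because the plan is silent: two-sided 5%, all 30 analysed, splits from 15/15 to 25/5, equal SD at both visits, and a visit 1 to visit 2 correlation r of 0.3 to 0.7.

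**Step 1: carry-over of a visit 1 difference.** If the groups differ by δ SD at visit 1 and nothing else separates them, the expected visit 2 difference is r × δ. The post-only t-test has noncentrality λ = rδ / √(1/n₁ + 1/n₂). At 15/15 the root is √(2/15) = 0.365, with 28 df and critical value 2.048.

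| δ | r | rδ | λ | Rejects, 15/15 | Rejects, 24/6 |
|---|---|---|---|---|---|
| 0.5 | 0.3 | 0.15 | 0.41 | 7% | 6% |
| 0.5 | 0.5 | 0.25 | 0.68 | 10% | 8% |
| 0.5 | 0.7 | 0.35 | 0.96 | 15% | 11% |
| 0.8 | 0.3 | 0.24 | 0.66 | 10% | 8% |
| 0.8 | 0.5 | 0.40 | 1.10 | 18% | 14% |
| 0.8 | 0.7 | 0.56 | 1.53 | 32% | 22% |

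(The λ column is for 15/15.)

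**Step 2: what adjustment does to power when the groups do not differ at visit 1.** Post-only: λ = 0.5 / 0.365 = 1.37. Adjusted: λ = 0.5 / (0.365 × √(1 − r²)), with 27 df and critical value 2.052. This gives λ = 1.44, 1.58 and 1.92 at r = 0.3, 0.5 and 0.7.

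| Split | Post-only | r = 0.3 | r = 0.5 | r = 0.7 |
|---|---|---|---|---|
| 15/15 | 26% | 28% | 33% | 46% |
| 20/10 | 24% | 26% | 30% | 41% |
| 25/5 | 17% | 18% | 21% | 28% |

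Read one-sided, as the directional wording might allow, post-only power is 38% at 15/15 and 26% at 25/5. If only the 80% of the retention criterion complete (24 dyads), two-sided power at 12/12 is 22%.

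**Step 3: what adjustment does when the groups already differ.** Take a visit 2 difference of 0.5 SD and a visit 1 difference of 0.5 SD, at 15/15. The adjusted difference is 0.5 − r × 0.5, which is 0.25 at r = 0.5 and 0.15 at r = 0.7. Then λ = 0.25 / (0.365 × 0.866) = 0.79 and 0.15 / (0.365 × 0.714) = 0.58, so power is 12% and 9%. Correlation between group and covariate inflates the variance by about 1 + 7.5 × 0.25 / 28 = 1.07 (where 7.5 = 15 × 15 / 30), which lowers these to 11% and 8%. The unadjusted test has 26%.

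**The case against.** Four points can be made for the plan as written.

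1. **The hypotheses are associations.** Neither says that the experiment causes the group difference. A lasting tendency of some adolescents to speak up is consistent with Hypothesis 4 as worded, so the 10% to 32% is a false-positive rate only for the question of a difference beyond the visit 1 level. This stands. A reader might infer that the plan would mistake a pre-existing difference for an intervention effect, but its wording makes no such claim. Adjustment therefore adds a second, narrower question and should not displace the first. Step 3 shows how far the two answers can part.
2. **Visit 1 is an imperfect baseline.** It rates an earlier decision and uses the interview guide rather than the stand-alone form. This stands too: r may be low, and adjustment may remove only part of a pre-existing difference. But Hypothesis 1 already treats visit 1 Child Express as a valid pre score, and the general DMIS change tests do the same for the scale. A paired change fixes the visit 1 slope at 1; a covariate model estimates it, which asks less of the score.
3. **Low power is no contradiction.** A reader might infer that using visit 2 scores alone is what makes these tests weak, or that the sample size statement is breached. Neither is supported. Power is low mainly because 30 dyads are split in two, it stays low after adjustment, and the 80% belongs to a future larger trial.
4. **This is a pilot.** True, but both items are listed as directional hypothesis tests, with no statement of precision.

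**Conclusion.** The point holds as one of interpretation. With visit 2 scores alone, a result for Hypothesis 3 or 4 cannot be attributed to the post-experiment decision rather than to how these families already behaved. The size depends on inputs that the plan does not give: for visit 1 differences of 0.5 to 0.8 SD, the rejection rate from carry-over alone at 15/15 runs from 7% to 10% at r = 0.3, up to 15% to 32% at r = 0.7. The documents establish neither that a visit 1 difference exists nor how large r is; they only make a difference plausible. The power gain from adjusting (26% to between 28% and 46% at 15/15) is secondary and applies only if the groups start level.

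**What to change.** In Hypothesis testing, for Hypotheses 3 and 4:

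- Keep the two-sample comparison and describe it as the association at visit 2.
- Pre-specify beside it a linear model of the visit 2 subscale on group plus the same reporter's visit 1 score on that subscale. For Hypothesis 3, fit it separately by reporter, or jointly with a dyad random intercept.
- Report both differences with 95% confidence intervals and label both hypotheses exploratory. State that the adjusted estimate concerns a difference beyond the visit 1 level, and that visit 1 rated an earlier decision in another format.
- Settle three definitions that either analysis needs: which subscale Hypothesis 3 means (its label does not match Joint/Options in item 12); whose report it uses; and which preferred-role answer forms the groups in Hypothesis 4, since the role is asked once at visit 1 and twice at visit 2.

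The cost is analysis wording and one degree of freedom, with no new data. The downside is a second estimate that may disagree with the first; stating in advance which question each one answers deals with that.
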